8.4.3 Follow-up of AE, SAE, and Other Reportable Safety Event Information

After the initial AE/SAE report, the investigator is required to proactively follow each participant at subsequent visits/contacts. All AEs, SAEs, and other reportable safety events, including pregnancy and exposure during breastfeeding, events of clinical interest (ECIs), cancer, and overdose will be followed until resolution, stabilization, until the event is otherwise explained, or the participant is lost to follow-up (as defined in Section 7.3). In addition, the investigator will make every attempt to follow all nonserious AEs that occur in allocated participants for outcome. Further information on follow-up procedures is given in Appendix 3: Adverse Events: Definitions and Procedures for Recording, Evaluating, Follow-up, and Reporting.

8.4.4 Regulatory Reporting Requirements for SAE

Prompt notification (within 24 hours) by the investigator to the Sponsor of SAE is essential so that legal obligations and ethical responsibilities towards the safety of participants and the safety of a study intervention under clinical investigation are met.

The Sponsor has a legal responsibility to notify both the local regulatory authority and other regulatory agencies about the safety of a study intervention under clinical investigation. The Sponsor will comply with country-specific regulatory requirements and global laws and regulations relating to safety reporting to regulatory authorities, IRB/IECs, and investigators.

Investigator safety reports must be prepared for suspected unexpected serious adverse reactions (SUSARs) according to local regulatory requirements and Sponsor policy and forwarded to investigators as necessary.

An investigator who receives an investigator safety report describing an SAE or other specific safety information (eg, summary or listing of SAE) from the Sponsor will file it along with the IB and will notify the IRB/IEC, if appropriate according to local requirements.

8.4.5 Pregnancy and Exposure During Breastfeeding

Although pregnancy and infant exposure during breastfeeding are not considered AEs, any pregnancy or infant exposure during breastfeeding in a participant (spontaneously reported to the investigator or their designee), including the pregnancy of a male participant's female partner, that occurs during the study are reportable to the Sponsor.

All reported pregnancies must be followed to the completion/termination of the pregnancy. Pregnancy outcomes of spontaneous abortion, missed abortion, benign hydatidiform mole, blighted ovum, fetal death, intrauterine death, miscarriage, and stillbirth must be reported as

serious events (Important Medical Events). If the pregnancy continues to term, the outcome (health of infant) must also be reported.

8.4.6 Disease-related Events and/or Disease-related Outcomes Not Qualifying as AEs or SAEs

This section is not applicable to this study.

8.4.7 Events of Clinical Interest (ECIs)

Selected nonserious and SAEs are also known as ECIs and must be reported to the Sponsor.

Events of clinical interest for this study include:

- An overdose of Sponsor's product, as defined in Section 8.5, that is not associated with clinical symptoms or abnormal laboratory results.
- An elevated AST or ALT lab value that is greater than or equal to 3X the upper limit of normal and an elevated total bilirubin lab value that is greater than or equal to 2X the upper limit of normal and, at the same time, an alkaline phosphatase lab value that is less than 2X the upper limit of normal, as determined by way of protocol-specified laboratory testing or unscheduled laboratory testing.*

*Note: These criteria are based upon available regulatory guidance documents. The purpose of the criteria is to specify a threshold of abnormal hepatic tests that must trigger an additional evaluation for an underlying etiology. The study site guidance for assessment and follow up of these criteria can be found in the Investigator Study File Binder (or equivalent).

It may also be appropriate to conduct additional evaluation for an underlying etiology in the setting of abnormalities of liver blood tests including AST, ALT, bilirubin, and alkaline phosphatase that do not meet the criteria noted above. In these cases, the decision to proceed with additional evaluation will be made through consultation between the study investigators and the Sponsor Clinical Director. However, abnormalities of liver blood tests that do not meet the criteria noted above are not ECIs for this study.

8.5 Treatment of Overdose

In the event that a participant has taken (accidentally or intentionally) any drug administered as part of the protocol that exceeds the dose as prescribed by the protocol, it is up to the investigator or the reporting physician to decide whether a dose is to be considered an overdose, in consultation with the Sponsor.

There is no specific guidance available regarding overdose with MK-8558, due to the lack of clinical experience with overdosing. In case of acute over-dosage, standard supportive care should be provided as clinically appropriate. The Sponsor clinical director should be contacted immediately.

8.6 Pharmacokinetics

The decision as to which plasma samples collected will be assayed for evaluation of PK/pharmacodynamics will be collaboratively determined by the Sponsor (e.g., samples at lower doses may not be assayed if samples at higher doses reveal undetectable drug concentrations). If indicated, these samples may also be assayed and/or pooled for assay in an exploratory manner for metabolites and/or additional pharmacodynamic markers.

8.6.1 Blood Collection for Plasma MK-8558

Sample collection, storage, and shipment instructions for plasma samples will be provided in the Study Operations Manual.

8.7 Pharmacodynamics

Sample collection, storage, and shipment instructions for pharmacodynamic samples (for HIV RNA measurement and viral resistance testing) will be provided in the Study Operations Manual.

8.8 Biomarkers

Collection of samples for other biomarker research is also part of this study. The following samples for biomarker research are required and will be collected from all participants as specified in the SoA:

- Blood for Genetic Analysis

8.8.1 Planned Genetic Analysis Sample Collection

The planned genetic analysis sample should be drawn for planned analysis of the association between genetic variants in DNA and drug response. This sample will not be collected at the site if there is either a local law or regulation prohibiting collection, or if the IRB/IEC does not approve the collection of the sample for these purposes. If the sample is collected, leftover extracted DNA will be stored for future biomedical research if the participant signs the future biomedical research consent. If the planned genetic analysis is not approved, but future biomedical research is approved and consent is given, this sample will be collected for the purpose of future biomedical research.

Sample collection, storage, and shipment instruction for planned genetic analysis samples will be provided in the Study Operations Manual.

8.9 Future Biomedical Research Sample Collection

If the participant signs the future biomedical research consent, the following specimens will be obtained as part of future biomedical research:

- Leftover DNA for future research
- Leftover main study plasma from MK-8558 assay stored for future research

8.10 Visit Requirements

Visit requirements are outlined in Section 1.3. Specific procedure-related details are provided in Section 8.

8.10.1 Screening

Approximately 4 weeks prior to intervention allocation/randomization, potential participants will be evaluated to determine that they fulfill the entry requirements as set forth in Section 5.

Participants may be rescreened after consultation with the Sponsor. Rescreening should include all screening procedures listed in the SoA, including consent review. Rescreen procedures cannot be conducted the day prior to intervention allocation/randomization if there are Day -1 procedures planned per protocol.

8.10.2 Treatment Period Visit

Refer to the SoA (Section 1.3) and Administrative and General Procedures (Section 8.1).

8.10.3 Discontinued Participants Continuing to be Monitored in the Study

At any point if a participant discontinues from treatment but continues to be monitored in the study, all of the study procedures specified in the SoA may be completed at the discretion of the investigator and with Sponsor agreement. The subset of study procedures completed will be communicated in a PCL.

8.10.4 Post-study

Participants will be required to return to clinic approximately 35 days after the last dose of study intervention for the post-study visit. If the post-study visit occurs less than 35 days after the last dose of study intervention, a subsequent follow-up telephone call should be made at 35 days post the last dose of study intervention to determine if any AEs have occurred since the post-study clinic visit.

8.10.5 Critical Procedures Based on Study Objectives: Timing of Procedure

For this study, the blood samples for plasma MK-8558 and HIV-1 viral RNA are the critical procedures.

At any post-dose time point, the blood sample for MK-8558 and the blood sample for viral RNA need to be collected as close to the exact time point as possible. All other procedures should be completed as close to the prescribed/scheduled time as possible. Study procedures can be performed prior or after the prescribed/scheduled time.

The order of priority can be changed during the study with joint agreement of the investigator and the Sponsor Clinical Director.

Any nonscheduled procedures required for urgent evaluation of safety concerns take precedence over all routine scheduled procedures.

The following variance in procedure collection times will be permitted.

- PK Collection as outlined in [Table 13](#).

Table 13 Blood Collection Windows for Plasma PK and HIV RNA

PK/PD Collection	PK/PD Collection Window
0 – <1.0 hr	5 min
1 - <24 hrs	15 min
24 - <48 hrs	2 hrs
48 - <96 hrs	4 hrs
96 – <168 hrs	8 hrs
≥168 hrs	24 hrs

- Pre-dose standard safety evaluations: vital signs and ECG at 3 hours; laboratory safety tests and physical exam at 24 hours
- Post-dose standard safety evaluations: vital signs, ECG, laboratory safety tests, and physical exam
 - <24 hours post-dose may be obtained within 30 minutes of the theoretical sampling time
 - 24 - <48 hours post-dose may be obtained within 2 hours of the theoretical sampling time

- 48 – <96 hours post-dose may be obtained within 4 hours of the theoretical sampling time
- 96 – <168 hours post-dose may be obtained within 8 hours of the theoretical sampling time
- \geq 168 hours post-dose may be obtained within 24 hours of the theoretical sampling time

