4 STUDY DESIGN

4.1 Overall Design

This is an open-label, single-dose, historical placebo-controlled, multiple panel trial of MK-8558 in participants with HIV-1 infection.

Up to four panels (Panels A-D), consisting of 6 participants per panel, will be enrolled. In each panel, participants will receive a single oral dose of MK-8558 (as outlined in [Table 1](#)) and undergo safety assessments and blood sampling for PK and viral load analysis.

[figure not shown]
Panels will be enrolled in a sequential manner, i.e., Panel B will initiate, and its dose level selected, following the review of safety, tolerability, viral dynamics, and PK data from Panel A (to at least 7 days post-dose). Similarly, selection of Panel C and D dose levels will occur following review of safety, tolerability, and viral dynamics data from Panels B and C, respectively, within this trial, and of emerging data from Protocol 001.

Data from the ongoing trial, MK-8558 Protocol 001 were used in the selection of the first dose (Panel A) with the inclusion of updated data within a previous substantial amendment (Protocol 002-01) to support the enrollment of Panels B, C and D.

In Panels A through C, study drug will be administered following at least a 10-hour fast. In Panel D, study drug will be administered following a standard breakfast. The fat content of this breakfast (i.e., high/moderate/low) will be determined based on the review of emerging safety and PK data from this study and from Protocol 001 and will be communicated in an official memo prior to dosing.

Following the treatment phase of the trial, participants will be encouraged to initiate an ART regimen

Because this is a Phase 1 assessment of MK-8558 in humans, the pharmacokinetic (PK), pharmacodynamic, and safety profiles of the compound are still being elucidated. This protocol is therefore written with flexibility to accommodate the inherent dynamic nature of Phase 1 clinical studies. Refer to Section 8.10.6 for examples of modifications permitted within the protocol parameters.

Specific procedures to be performed during the study, as well as their prescribed times and associated visit windows, are outlined in the SoA in Section 1.3. Details of each procedure are provided in Section 8.

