6.3 Measures to Minimize Bias: Randomization and Blinding

6.3.1 Intervention Assignment

Participants in this study will be assigned to panel and treatment according to an allocation schedule. A sample allocation schedule is shown in [Table 11](#).

Table 11 Sample Allocation Schedule

Panel	N	Dose of MK-8558 ^a			
A	6	400 mg			
B ^b	6		≤900 mg		
C ^b	6			≤1600 mg	
D ^b	6				≤1600 mg with food

a. Doses may be adjusted downward following review of safety and viral load data from preceding panels.
b. The doses to be administered in Panels B, C and D will be based on the results of safety and viral load data out to at least Day 8 in Panels A, B and C, respectively.

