6.6 Dose Modification (Escalation/Titration/Other)

Prior to proceeding to the next panel, the following data from at least 4 evaluable subjects from the previous dosing panel will be reviewed:

- key safety data including vital signs, 12-lead ECGs, laboratory safety tests, and AEs from the previous dose levels up to at least 168 hours post dose
- viral dynamic data (out to 168 hours post-dose)

Before proceeding to Panel B, PK data from Panel A (a minimum of 4 evaluable subjects) will be reviewed to compare PK from HIV-infected participants with PK observed in healthy participants in Protocol 001, to ensure that doses selected for Panel B are appropriate from both efficacy and safety standpoints.

In addition, safety, tolerability, and PK data from doses up to 1600 mg (including a food-effect assessment) from the ongoing Protocol 001 have been reviewed and support the proposed dosing for Protocol 002.

Based on the review of data (specified above), modifications to planned dosing may be implemented, including:

- administration to a subsequent panel the same dose level to further evaluate that particular level;
- administration of a lower dose of the study treatment;
- administration of the same or lower dose as a divided dose; or
- administration of the same or a lower dose with or without food.

Or, dosing may be stopped. Participant discontinuation criteria are outlined in Section 7.

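### Can a 168-hour visit held early, but within its permitted window, fall short of the data needed to open the next panel?

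*Combined protocol and SAP*

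**What the plan says.** Section 8.10.5 sets collection windows that widen with time after dosing. For safety evaluations in the last band, those at "168 hours post-dose may be obtained within 24 hours of the theoretical sampling time". The table headed "Table 13 Blood Collection Windows for Plasma PK and HIV RNA" applies the same 24 hours to PK and viral load samples from 168 hours onward. Procedures may be early or late, but the section also sets a target. The PK and viral RNA samples "need to be collected as close to the exact time point as possible", and for the rest, "All other procedures should be completed as close to the prescribed/scheduled time as possible".

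The review before the next panel is described in three places:

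- Section 6.6: "the following data from at least 4 evaluable subjects from the previous dosing panel will be reviewed". The safety data come "from the previous dose levels up to at least 168 hours post dose". The viral dynamics data are to extend to 168 hours, and for these the section does not use minimum wording.
- Section 6.3.1, Table 11 footnote b: doses for Panels B, C and D rest on "results of safety and viral load data out to at least Day 8 in Panels A, B and C, respectively".
- Section 4.1, for Panel A before Panel B: safety, tolerability, viral dynamics and "PK data from Panel A (to at least 7 days post-dose".

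Section 8.3.2 puts the pre-dose vital signs on Day 1, so the dosing day is Day 1.

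**The concern.** Two of the cut-offs are given in days and all three locations use minimum wording, whereas the Schedule of Activities is laid out in hours. Someone counting actual elapsed time would see that a visit permitted by 8.10.5 can take place at 144 hours, on Day 7, and so before the stated minimum. No visible sentence says whether such a visit counts.

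What would be at stake is the basis for opening the next panel. Safety laboratory tests are the most exposed item: after the 168-hour visit, the next scheduled set is at the post-study visit, about 35 days after dosing. If the review began with exactly four evaluable participants, one early visit could raise a question about whether the requirement was met.

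**Working it through.** **Do the cut-offs agree?** Section 6.6 gives 168 h. Dividing, 168 / 24 = 7 days post-dose, the figure in 4.1. With dosing on Day 1, 1 + 7 = Day 8, the figure in 6.3.1. All three state one nominal time point.

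**What does the window allow?** 168 − 24 = 144 h (6 days post-dose, Day 7) and 168 + 24 = 192 h (8 days post-dose, Day 9). The largest early shortfall on actual time is 24 h.

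**Could another visit be meant?** The neighbouring columns in the Schedule of Activities, with their windows from 8.10.5, are:

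| Scheduled time | Window | Permitted range |
|---|---|---|
| 120 h | ±8 h | 112 to 128 h |
| 168 h | ±24 h | 144 to 192 h |
| 240 h | ±24 h | 216 to 264 h |

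The ranges do not overlap. A scheduled sample taken within window between 144 and 192 h can only be the 168-hour sample.

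**How much of the window falls on Day 7?** Section 8.1.8.1 says dosing is in the morning. No clock time is given, so assume 07:00 to 11:00. Calendar Day 8 then begins at 7 × 24 − 7 = 161 h down to 7 × 24 − 11 = 157 h post-dose. The part of the window on Day 7 is 161 − 144 = 17 h down to 157 − 144 = 13 h, out of 48 h. That is a share of the window's width, not a probability. A draw a few hours early but on Day 8 meets 6.3.1 even when read by the calendar.

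**How many early visits would matter on the strict reading?** Each panel has 6 participants and 6.6 requires 4 evaluable. Since 6 − 4 = 2, a complete panel can have two participants seen too early and still supply four. A third leaves 6 − 3 = 3.

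**Is there a way to fill a shortfall?** The post-study visit is at about 35 × 24 = 840 h, so scheduled laboratory tests would not fill it in time. But section 8 allows repeat or unscheduled samples for safety reasons, and Appendix 2 allows additional tests when the investigator judges them necessary. HIV RNA has a scheduled draw at 240 h, adverse events are reviewed throughout, and PK review is required only between Panels A and B.

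**Would the window distort C168hr?** Only if nominal times replaced actual sampling times. Section 5.1 equates 35 days with five terminal half-lives, implying 35 / 5 = 7 days, or 168 h. At the window edges, 2^(24/168) − 1 = +10.4% and 2^(−24/168) − 1 = −9.4% in one participant. No visible text says nominal times are used. The PK/PD methods in 9.6 are redacted, and 9.1 refers to a fuller SAP. This gives no evidence of an error.

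**The case for a change.** The best case for the concern is that a cut-off worded as a minimum reads more naturally as elapsed time than as a visit label, above all where it is stated in days. A site following 8.10.5 and a colleague applying the Table 11 footnote could disagree in good faith. The 2-of-6 margin shrinks if a participant drops out or if the review starts as soon as four have data. Unscheduled sampling is a case-by-case remedy and does not say what the cut-off means.

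Some of this stands. The arithmetic is right, and no visible sentence links the window to the review cut-offs. But the elapsed-time reading treats a sample that complies with the protocol as missing, and nothing in 4.1, 6.3.1 or 6.6 asks for that. The day wording adds no second time point, because 7 days is exactly 168 hours and Day 8 is the day on which it falls. What remains is a convention that could have been spelled out.

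**Conclusion.** The plan is consistent on this point. Section 8.10.5 defines its windows as permitted variation around a theoretical sampling time, and the three review cut-offs name a single scheduled time point, 168 hours. A visit inside the window supplies the data for that time point.

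If the cut-offs were nevertheless read on actual time, the shortfall would be at most 24 hours. In a complete panel it would take three early visits to bring the count below four, and the protocol already permits extra samples. No endpoint, sample size, power or error rate changes.

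This conclusion rests on the cut-offs referring to the scheduled time point, which is the usual reading of a visit window, and on Day 1 being the dosing day. The calendar figures also assume dosing between 07:00 and 11:00, but the conclusion does not depend on them.

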8.10.6 Study Design/Dosing/Procedures Modifications Permitted Within Protocol Parameters

This is a Phase 1 assessment of MK-8558 in humans, and the PK, pharmacodynamic, and safety profiles of the compound is still being elucidated. This protocol is written with some flexibility to accommodate the inherent dynamic nature of Phase 1 clinical studies. Modifications to the dose, dosing regimen, and/or clinical or laboratory procedures currently outlined may be required to achieve the scientific goals of the study objectives and/or to ensure appropriate safety monitoring of the study participants.

As such, some alterations from the currently outlined dose and/or dosing regimen may be permitted based on newly available data, but the maximum daily dose may not exceed those currently outlined in the protocol.

- Repeat of or decrease in the dose of the study intervention administered in any given period/panel
- Entire period(s) or panel(s) may be omitted
- Adjustment of the dosing interval (e.g., divided doses [QD to BID, TID])
- Remove a planned PK pause if agreed by Sponsor and investigator if no further increases in total daily dose
- Addition of PK pause
- Instructions to take study intervention with or without food or drink may also be modified based on newly available data
- Modification of the fed cohort to another panel. In the event that this modification is implemented, the planned dosing and feeding regimen with supporting data will be communicated in an official memo.
- Modification of the PK/pharmacodynamic sample processing and shipping details based on newly available data or for operational reasons

The PK/pharmacodynamic sampling scheme currently outlined in the protocol may be modified during the study based on newly available PK or pharmacodynamic data (e.g., to

obtain data closer to the time of peak plasma concentrations). If indicated, these collected samples may also be assayed in an exploratory manner for metabolites and/or additional pharmacodynamic markers.

Up to additional 50 mL of blood may be drawn for safety, PK, and/or pharmacodynamic analyses. The total blood volume withdrawn from any single participant will not exceed the maximum allowable volume during his/her participation in the entire study (Section 8).

The timing of procedures for assessment of safety procedures (e.g., vital signs, ECG, safety laboratory tests, etc.) may be modified during the study based on newly available data. Additional laboratory safety tests may be added to blood samples previously drawn to obtain additional safety information. These changes will not increase the number of study procedures for a given participant during his/her participation in the entire study

It is understood that the current study may employ some or none of the alterations described above. Any alteration made to this protocol to meet the study objectives must be detailed by the Sponsor in a letter to the Study File and forwarded to the investigator for retention. The letter may be forwarded to the IRB/IEC at the discretion of the investigator.

